While injury rates, hormones, and some motor control patterns diverge around puberty, it is unclear how such changes increase the risk of ligament injury. Neuromuscular control is influenced by fluctuations in estradiol and progesterone during the menstrual cycle, but the mechanism of this interaction remains unknown. Post-pubertal females have shown variable muscle activation patterns of the gluteus maximus and semitendinosus during a landing task that correlate with cyclic variations in estradiol. Neuromuscular control during hopping also fluctuates with hormone changes, but not in women with more stable levels of estradiol and progesterone induced by monophasic oral contraceptives. To fill the current research gap, we propose to determine the hormonal regulation of different constituents of neuromuscular control.

Our project will increase understanding in four realms. First, we propose a paradigm shift, arguing that increased rates of injury in females is not due to direct changes in cycle specific connective tissue properties, but are secondary to hormone mediated changes in neuromuscular control. Second, we will determine if our muscle stretch reflex protocol can identify hormone-mediated alterations in joint control. If so, this protocol can be employed to determine whether this process causes joint injury. Due to its technical simplicity, the protocol and the associated equipment (hammer/load cell/wireless EMG unit and a tablet) can be used in clinical settings and at athletic training sites, facilitating large-scale examination of the neuromuscular underpinnings of joint injuries. Importantly, our pilot data showed a significant change in the reflexes (on average, up to 2.5 folds reductions) from the luteal to the ovulatory phase, highlighting the robustness of the test in detecting changes in reflex excitability, which may be applicable to multiple clinical settings. Third, our findings should allow clinicians to time neuromuscular retraining programs to certain points during maturation or the menstrual cycle when females might be most receptive to reprogramming neuromuscular control strategies. Similarly, identifying a cortical level locus of sex hormone mediated changes in neuromuscular control would inform the implementation and timing of motor learning specific strategies. Fourth, by including

Form A

IRB Velos	STU-2018-0192 26783
--------------	------------------------

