At each session, subjects will be seated in an experimental chair with their right hip and knee positioned in 90° of flexion. The ankle joint will be secured in a coupling ring, which will fix the limb to a load cell, via a rigid beam. Pre-amplified surface electromyography will be placed along the lower limb muscles. In an effort to ensure the same electrode placement at subsequent testing sessions, each electrode site will be marked with a permanent marker and subjects will be encouraged not to wash off the markings between sessions. Three maximum voluntary contractions (MVCs) will be recorded with a minimum of 10 seconds of rest between trials. The muscle reflex will be evoked by tapping the patellar tendon with a hammer instrumented with a load cell. The load cell instrumented hammer will allow us to quantify the reflex gain by normalizing the reflex EMG by the tap force. The hammer will be fixed on a pendulum to standardize the tap force and tap rate used to elicit the reflexes. For each pre-activation level (0%, 5%, 10%, and 20% knee extension torque at MVC), up to 40 total taps will be delivered during each testing session. Taps will be randomly spaced (varying from 10-20 seconds between taps) to limit the subjects' ability to anticipate the timing of the next tap. In an attempt to further minimize supraspinal modulation of the observed tap induced muscle activity at rest (0% MVC), subjects will be instructed to relax and maintain a standardized position. Finally, to assess the joint's connective tissue response at varying points in the cycle, anterior knee laxity (AKL) will be measured with the knee arthrometer.

AIM 2: Determine the influence of sex hormone fluctuations on spinal motor neuron excitability

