All necessary data pertaining to the study from SRAlab will be transferred to UT Southwestern Medical Center. Data (except for blood samples) will be maintained for future use, for indefinite amount of time. All data would be de-identified and stored in a protected database. Researchers only with IRB approval and approval from authorized personnel of this study, would have access to the controlled database of data, to be used to answer questions related specifically to their research study.

SAMPLE SIZE JUSTIFICATION

AIMS 1 and 2: We wish to rule out an effect of hormonal state on motor neuronal excitability. To do this, specified the minimum effect size that we considered meaningful along with high statistical power that minimized the chances of a Type-I error. We conducted statistical simulations to evaluate this scenario. Pooling $N = 30$ OCs and $N = 30$ nOCs that provide daily H-reflexes from soleus muscle (Aim 1) and MSR from 3 quadriceps muscles (VM, VL, RF) over one menstrual cycle provided power = .95 to detect effects as small as an average within-individual correlation of $r = -0.075$ ($R^2 = .005$) between a single hormone and reflex responses across a range of situations. Smaller differences are considered as pragmatically meaningless. This degree of power holds even if menstrual cycles vary from 22 to 32 days, and participants miss an average of 25% (see above) of their lab visits (and assumes the data are missing at random).

AIM 3: To test hypothesis 3, that estradiol will produce a targeted facilitatory influence on lower limb muscles, we used a GEE model that views the mean conditioned MEPs at each ISI as correlated outcomes before separate post-hoc tests for each inter-pulse interval (ISI = 7, 10, 15, 20, 25, 30 ms) and each subject between peak estradiol and baseline hormone concentration (Fig. 7). This synthesis establishes a within-

Form A

IRB Velos	STU-2018-0192 26783
--------------	------------------------

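### Aim 1's active-state reflex gain is matched on net knee torque and normalised only by tap force, so variation in pre-tap quadriceps activity stays in it as noise and, if it tracks hormones, cannot be told apart from reflex change.

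*Combined protocol and SAP*

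**What the plan says.** Section 4.a, Aim 1, defines the recording conditions by torque: "For each pre-activation level (0%, 5%, 10%, and 20% knee extension torque at MVC"). Torque is taken at one point: "The ankle joint will be secured in a coupling ring, which will fix the limb to a load cell, via a rigid beam". The reference contraction is among the procedures for each session: "Three maximum voluntary contractions (MVCs) will be recorded with a minimum of 10 seconds of rest between trials". The text does not say which trial, or which session's value, sets the target.

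For EMG, "Pre-amplified surface electromyography will be placed along the lower limb muscles". The Sample Size Justification names three quadriceps muscles (VM, VL, RF). The instrumented hammer is there to "quantify the reflex gain by normalizing the reflex EMG by the tap force". No other divisor, covariate or EMG window is given for Aim 1. The one related safeguard applies to the relaxed state only: "at rest (0% MVC), subjects will be instructed to relax and maintain a standardized position".

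Two other places bear on this. The Aim 2 text standardises how active the muscle is, because a change in it can alter the size of a spinal reflex. The Sample Size Justification sets the smallest correlation of interest for Aims 1 and 2 at -0.075 within a woman, and adds: "Smaller differences are considered as pragmatically meaningless".

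**The concern.** A load cell fixed to the limb at the ankle reads net joint torque, extensors minus flexors. Holding that constant does not hold quadriceps activation constant. If the hamstrings pull harder, the quadriceps must work harder to reach the same reading. By the protocol's own reasoning in Aim 2, a more active muscle can give a different reflex. Dividing by tap force corrects for the size of the tap, not for the state of the muscle when the tap arrives.

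Two consequences follow, of different standing:

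- **Certain in kind, unknown in size.** Session-to-session variation in background activity goes into the active-state gain as noise, although the pre-tap EMG could remove much of it.
- **Conditional.** If that variation moves with estradiol or progesterone, an active-state hormone effect could be a change in background drive, a change in reflex excitability, or both. The two could also cancel. The project aims to locate hormone effects at distinct levels of motor control, and the gain as stated could not do that for the active state.

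**Working it through.** **The plan's own figure.** The plan claims power 0.95 to detect r = -0.075. A Fisher-z approximation (two-sided 5% assumed, 60 women, 27 days, daily sampling, 25% missed) gives an effective n of 60 × (0.75 × 27 - 1) = 1,155 and power 0.72 for one outcome. Pooling four muscles gives 0.97 or 0.90 if the inter-muscle correlation is 0.25 or 0.5. So 0.95 is attainable but cannot be confirmed, because neither alpha nor that correlation is stated. This point does not dispute the figure; 0.075 serves only as a yardstick.

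**Assumed inputs (the documents give none).** Reflex rise per 1% rise in background EMG, e = 0.5 to 1.0%. Session-to-session CV of background EMG, 10 to 20%. Within-woman CV of the reflex, 30 to 40%. Background-hormone correlation, c = 0.2 to 0.3, or zero.

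**Induced correlation** = e × CV(background) × c / CV(reflex).

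- Low end: 0.5 × 10 × 0.2 / 40 = 0.025.
- High end: 1.0 × 20 × 0.3 / 30 = 0.20.
- With c = 0 it is 0.

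**Removable share of outcome variance** = (e × CV(background) / CV(reflex))², whatever the value of c.

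- Low end: (0.5 × 10 / 40)² = 0.016, about 2%.
- High end: (1.0 × 20 / 30)² = 0.444, about 44%.

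**Simulation.** 60 women × 10 sessions (27 / 2 × 0.75 is about 10), two-sided 5%, 1,500 replicates, within-woman centred regression, and no hormone effect on the reflex at fixed background activity:

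| e | CV background | c | CV reflex | Induced r | Hormone term significant, no covariate |
|---|---|---|---|---|---|
| 0.5 | 10% | 0.2 | 30% | 0.033 | 11% |
| 1.0 | 10% | 0.2 | 40% | 0.050 | 19% |
| 0.5 | 15% | 0.3 | 30% | 0.075 | 42% |
| 1.0 | 15% | 0.3 | 30% | 0.150 | 94% |

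A repeat with 2,000 replicates gave 12, 22, 40 and 95%. With c = 0 the rate was nominal (5.7%). With background EMG as an error-free covariate it was 4 to 6%. With covariate reliability 0.7, the third and fourth rows fall only to 9% and 23%; at reliability 0.5, to 15% and 48%.

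**Is the mechanism large enough?** At fixed net torque T, quadriceps torque is T plus hamstring torque. If hamstring torque is 10% of T and rises by half, quadriceps torque changes by 1.15 / 1.10 - 1 = 4.5%. Over hamstring shares of 5 to 20% and rises of 25 to 50%, the range is 1.2 to 8.3%. For comparison, with a reflex CV of 30% and an artefact correlated 0.5 with the hormone, r = 0.075 needs an artefact SD of 0.075 × 30 / 0.5 = 4.5% of mean gain. These are the same order of size, but all of these inputs are assumed.

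**The case against.** The case against a stronger claim is good, and most of it stands.

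- **No evidence of a hormone link in this task.** Section 2.a reports "variable muscle activation patterns of the gluteus maximus and semitendinosus during a landing task that correlate with cyclic variations in estradiol". A reader might infer that the sponsor expects hamstring activity to follow estradiol in Aim 1. That evidence is from landing; Aim 1 is a seated hold with the limb fixed, at no more than 20% of MVC. Every raised rate in the table presupposes a non-zero link.
- **The extreme row is demanding.** It needs background EMG to shift 0.3 × 15 = 4.5% per hormone SD, or 9 to 13.5% over 2 to 3 SD, against 1.2 to 8.3% from the co-contraction example. The first two rows induce correlations below 0.075.
- **Session MVC.** A reader might infer that a higher session MVC by itself confounds the gain because the absolute target rises. It does not: if contractile capacity has risen and the target is reset that day, relative effort is largely preserved. A problem would need a change in voluntary drive, or a fixed MVC reference under changing capacity, and the text does not say which reference is used.
- **Mediation.** If hormones change background drive, that is itself a hormone effect on motor control, and the reflex at matched torque is a legitimate total effect. This is right, and is why both results are needed.
- **General brevity.** The tap-force sentence says what the hammer allows and is not an exclusive definition. The form gives no Aim 1 model at all. That is fair, but it leaves the adjustment to be chosen after the data are seen.
- **Existing protection.** The 0% level has no torque target, so a hormone effect there is not explained by torque matching, and the graded levels allow rest and activity to be compared.

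None of this supplies a match or adjustment for pre-tap quadriceps activity at the 5, 10 and 20% levels.

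**Conclusion.** The point holds for the active levels, as a gap in the stated analysis. Aim 1 fixes net torque, states only a tap-force normalisation, and leaves pre-tap quadriceps activity uncontrolled, although the protocol says elsewhere that activation matters for reflex size. The removable variance is about 2 to 44% under the assumed inputs. If background activity tracks hormones with correlation 0.2 to 0.3, the induced correlation is 0.025 to 0.20, a range that includes the plan's 0.075. If it does not, there is no bias.

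A reader might infer that Aim 1's active-state results are confounded, with false-positive rates as high as 94%. The documents do not support that: they show that the problem is possible, not that it occurs or how large it is. Nor is every such result false, since at matched torque it may be a real total effect. What cannot be supported from the stated gain alone is calling an active-state effect a change in reflex excitability. The change is worth making because it is cheap and must be fixed before the data are seen.

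**What to change.** 1. For each tap, compute mean rectified EMG of the same quadriceps muscle in a fixed window just before the tap. State the window, and that the stored trace starts early enough to contain it.
2. For the 5, 10 and 20% levels, prespecify a model of reflex EMG on hormone with within-woman pre-tap EMG and tap force as covariates (matched activation).
3. Report beside it the result without pre-tap EMG (total effect at matched torque). Do not describe an active-state effect as a change in reflex excitability unless it persists after adjustment.
4. State that measurement error in pre-tap EMG makes the adjustment partial.
5. At 0%, use the same window to exclude taps with background activity above a preset limit.

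The cost is analysis-plan wording and signal processing on EMG that the plan already records, with no extra visits, taps or participants. The downside is one more model term and two results to report and explain.

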The goal of this project is to test our central hypothesis that changes in sex hormone concentration result in changes to the basic elements of motor control – at multiple levels, from the musculotendinous unit to motor control circuitry. Under Aim 1 we will determine the influence of sex hormone fluctuations on the muscle stretch reflex during active and passive states, and the time lag between hormone concentration changes and the reflex response. We will use a technically simple assessment that could be implemented in the field. Under Aim 2 we will determine the influence of sex hormone fluctuations on spinal motor neuron excitability using H-reflex as a probe and the simultaneous change in the muscle mechanics using muscle twitch response. Aims 1 & 2 will include a focus on the differential role of oral contraceptives. In Aim 3 we will use paired-pulse transcranial magnetic stimulation during active contraction to determine the influence of sex hormone fluctuations on cortical excitability in naturally cycling women. In the basic elements of motor control explained in Aim 2 and Aim 3 is that the sex hormones modulate the synaptic transmission and plasticity of neuron and muscles. The modulation of the synaptic transmission and plasticity of neuron and muscles might be caused by the changes of the neurotransmitter or muscle fiber in the transcriptional level, translational level, or combination of both. In Aim 4, we want to explore these changes through sequencing of whole exome and microRNA in addition to evaluating the expression level of mRNA and proteins related to synaptic transmission and muscle. Our findings have the potential to guide future research in injury prevention strategies, including targeted neuromuscular training. This knowledge will enable clinicians to educate female patients on neuromuscular effects of sex hormones during times of high fluctuations, including puberty, pregnancy, and menopause.

Abbreviations:

nOC = non- users of oral contraceptives

OC = oral contraceptive users

2. Background.

- Describe past experimental and/or clinical findings leading to the formulation of your study.
- For research involving investigational drugs, describe the previously conducted animal and human studies.
- For research that involves FDA approved drugs or devices, describe the FDA approved uses of this drug/device in relation to your protocol.

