women taking hormonal contraceptives, we will determine if, and to what extent, endogenous and exogenous estradiol and progesterone have different effects on knee neuromechanics.

It has been suggested that oral contraceptives might prevent musculoskeletal injury in female athletes, but there is a paucity of literature to guide clinicians in this area. As 40-70% of female collegiate basketball and soccer players [more than 10 million women in the United States, and 100 million women worldwide] report taking oral contraceptives, understanding their effects on the neuromusculoskeletal system is critical. Answering these questions has the potential to reduce the risk and rates of ACL injury and mitigate the long- term knee pain in future generations of female athletes. While our focus is on basic neuromuscular changes due to natural hormone fluctuations, we expect that this knowledge will illuminate other effects of sex hormones on the neuromusculoskeletal system, such as in osteoarthritis in perimenopausal women or lumbopelvic control in peripartum females.

Most studies have focused on hormonal modulation of the passive mechanics of connective tissues, measured in humans at the aggregate joint scale. Such studies have yielded conflicting results. Instead, we argue that sex hormones may have a more significant effect on active properties of the neuromuscular system. We suggest the injury sex disparity is likely due to changes in neuromuscular control rather than in aggregate joint stiffness. To the best of our knowledge, this study will be the first to examine, simultaneously, hormonal effects in the musculotendinous unit (Aim 1), motor neuron (Aim 2), and cortical motor neuronal networks (Aim 3), which are key contributors to movement control. This project builds a foundation for the study of sex differences in neurophysiologic properties of cortical networks.

b. Current practice

N/A

3. Study Design.

Describe the study design (e.g., single/double blind, parallel, crossover, etc.) Consider inserting a scheme to visually present the study design.

Same as #4 below.

4. Research Plan / Description of the Research Methods:**4.a. Provide a comprehensive narrative describing the research methods.**

- 1) Provide the order in which tests/procedures will be performed,
- 2) Provide the setting for these events and a description of the methods used to protect privacy during the study.

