- 3) Provide the plan for data analysis (include as applicable the sample size calculation)

Please respond to all components of this item, or clearly indicate which components are not applicable.

STUDY TIMELINE:

Form A

IRB Velos	STU-2018-0192 26783
--------------	------------------------

month	Year 1			Year 2			Year 3			Year 4			Year 5		
	1-3	4-11	12	1-5	6	7-11	12	1-5	6	7-11	12	1-5	6	7-11	12
Set-up, hiring															
Recruitment															
Testing															
Project Meeting															
Data Analysis															
Conferences															
Manuscripts															

PROCEDURES INVOLVED:

The sequence of experiments is shown in Fig. 1. During month one, all eumenorrheic subjects (nOCs), will provide blood samples every other day to track their hormones across the menstrual cycle (they will track menstrual cycle for 2-3 months prior). Post hoc analyses will compute subject-specific hormonal fluctuations throughout the month using a nonlinear mixed-effect model. nOCs will use urinary ovulation kits to verify that they have ovulatory cycles and identify the approximate day of ovulation. nOCs and male controls will have a brain MRI to establish consistent coil placement across visits in Aim 3, where TMS will be used to assess cortical excitability.

In month 2, all female subjects, both OCs and nOCs, will undergo every other day testing as described in Aims 1 and 2 (described in detail below) and provide every other day blood samples. nOC subjects will use urinary ovulation kits daily as described above. Hormone concentrations of each nOC subject will be compared to the subject-specific mixed-effect model from month one to determine where she is in her menstrual cycle. This estimation will enable TMS testing at six key points during the cycle (Aim 3). For example, when the subject's daily estradiol concentrations are rising and the model indicates that her peak estradiol should occur the next day, she will be instructed to report to the lab for TMS testing in the next 24 hours. On these days, she will complete the protocols for Aims 1-3. Subjects will be randomized to start testing in the follicular, peri-ovulatory, or luteal phase where Day 1 is defined as the first day of menses.

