The time required for each experiment, including setup, is approximately 2½ to 3 hours for Aims 1 and 2 combined and 2 - 3 hours for Aim 3. The investigator will be blinded to menstrual cycle phase and contraceptive use. The comparative groups for Aims 1 and 2 will be women on monophasic oral contraceptives containing progestins of similar potency and androgenicity, as justified by our published and pilot data. The control group for all Aims will be age-matched healthy males. Our choice of males as

[figure not shown]

Figure 1. Sequence of experiments. In month one, non-users of oral contraceptives will have their blood drawn to determine their hormonal signature. In month two, subjects will undergo daily blood draws as well as testing for Aims 1 and 2. Subjects will complete tests for Aim 3 on six occasions defined by key hormonal fluctuations.

Form A

IRB Velos	STU-2018-0192 26783
--------------	------------------------

controls for Aim 3 is motivated by the lack of data to guide interpretation of the effects of exogenous hormones on cortical circuitry.

Below is the specific experimental protocol for each AIM:

AIM 1: Determine the influence of sex hormone fluctuations on muscle stretch reflex at relaxed and active states.

Venipuncture will be performed at UT Southwestern Medical Center or UT Southwestern Lab. Venipuncture will be completed every other day during a full menstrual cycle, for a total of 2 cycles. This equates to 28 to 40 blood draws total (not necessarily consecutively), up to 3.04 teaspoons of blood per draw, for a maximum of 85.12 to 121.6 teaspoons (425.6 ml to 608 ml) over the course of study participation (2 – 3 months, equivalent to 2 menstrual cycles). To minimize the effect of diurnal fluctuations of hormone levels, testing will be done at a consistent time of day for each test session across all Aims. Furthermore, OCs will be asked to ingest their birth control pill at a consistent time each every day of the testing.

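### Aims 1 and 2 have power only for a pooled OC + nOC average; the stated OC-versus-nOC contrast has neither an analysis nor power, and a pooled null need not hold in naturally cycling women

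*Combined protocol and SAP*

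**What the plan says.** The sample size justification for Aims 1 and 2 (Section 4.a) opens with its purpose: "We wish to rule out an effect of hormonal state on motor neuronal excitability". The supporting simulation is described as "Pooling $N = 30$ OCs and $N = 30$ nOCs that provide daily H-reflexes from soleus muscle", together with stretch reflexes from three quadriceps muscles over one cycle. It claims power .95 for an average within-woman correlation of -0.075 between a single hormone and the reflex, and treats anything smaller as of no practical interest.

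The contrast between the groups appears in three other places:
- The statement of aims before Section 2: "Aims 1 & 2 will include a focus on the differential role of oral contraceptives".
- Section 2.a, Background: the study is to find out whether, and how far, "endogenous and exogenous estradiol and progesterone have different effects on knee neuromechanics".
- Section 4.a, Procedures Involved: "The comparative groups for Aims 1 and 2 will be women on monophasic oral contraceptives".

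Section 2.a also gives a reason to think the groups might differ. It reports that neuromuscular control in hopping varies with hormones, "but not in women with more stable levels of estradiol and progesterone induced by monophasic oral contraceptives".

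The documents name no model for the reflex outcomes. The one mixed model describes the hormone profiles: "Post hoc analyses will compute subject-specific hormonal fluctuations throughout the month using a nonlinear mixed-effect model". The GEE model belongs to Aim 3.

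**The concern.** A pooled average and a difference between groups are separate questions. The plan asks both and supplies a basis only for the first. Two consequences follow.

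First, the .95 does not carry over to the OC-nOC difference, which is always estimated less precisely than the pooled average.

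Second, because the declared purpose is to rule out an effect, a null result would be interpreted. If only naturally cycling women show an association, pooling with OC women shrinks it. An nOC association of the size the plan calls meaningful could then sit behind a pooled result that looks like no effect. If the association is the same in both groups, pooling costs nothing.

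**Working it through.** **Inputs.** From Section 4.a: 30 OC and 30 nOC women, power .95, r = -0.075, cycles of 22 to 32 days, 25% of visits missed, daily reflexes. Assumed: two-sided alpha 0.05 (neither alpha nor sidedness is stated for these aims). Scenario: nOC r = -0.075, OC r = 0.

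**1. The plan's .95.** An approximation is power = Φ(r/√(1 - r²) × √n_eff - 1.960), with n_eff = 60 × (visits - 1) × m/(1 + (m - 1)ρ) for m muscles with between-muscle correlation ρ. At the midpoint of 27 days, visits = 27 × 0.75 = 20.25, so one muscle gives n_eff = 60 × 19.25 = 1155 and power .72. Four independent muscles give .999. Four muscles with ρ = 0.3, 0.35 and 0.5 give .96, .95 and .90. Power .95 needs n_eff of about (3.605/0.075)² = 2310, or about two muscles' worth of independent data. The figure is plausible but cannot be reproduced exactly, because ρ and the between-woman variation are not given. It is taken as correct from here on.

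**2. Pooled standard error implied by .95.** 1.960 + 1.645 = 3.605; SE = 0.075/3.605 = 0.0208.

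**3. Splitting by group.** Let w be the share of the pooled weight carried by nOC women, with the pooled SE held fixed. Then SE(nOC) = SE/√w and SE(difference) = SE/√(w(1 - w)). Equal weights fit an average of within-woman correlations. A pooled slope could lean towards nOC women, whose hormones vary more. The text does not say which applies, so a range is shown.

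| Quantity | w = 0.5 | w = 0.7 | w = 0.9 |
|---|---|---|---|
| SE(nOC) | 0.0294 | 0.0249 | 0.0219 |
| SE(difference) | 0.0416 | 0.0454 | 0.0694 |
| Pooled mean, w × (-0.075) | -0.0375 | -0.0525 | -0.0675 |
| Pooled power, Φ(3.605w - 1.960) | .44 | .71 | .90 |
| nOC-alone power, Φ(3.605√w - 1.960) | .72 | .85 | .93 |
| Power for a difference of 0.075, Φ(3.605√(w(1 - w)) - 1.960) | .44 | .38 | .19 |
| Difference detectable at 80% power, 2.802 × SE(difference) | 0.117 | 0.127 | 0.194 |

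The value 0.075 is the plan's threshold for the average; it serves here only as a reference size for the difference.

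**4. If a rule-out were read from a pooled 90% interval inside ±0.075.** The half-width is 1.645 × 0.0208 = 0.0342, so the estimate must lie within ±0.0408. Under the nOC-only scenario this happens with probability .56, .29 or .10 for w = 0.5, 0.7 or 0.9. With a 95% interval it is .44 at w = 0.5 and .19 at w = 0.7.

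**5. One-sided alpha 0.05 instead, equal weights.** SE = 0.075/3.290 = 0.0228. Pooled power with an nOC-only effect is .50, nOC-alone power .75, power for a difference of 0.075 .50, and the detectable difference 0.113.

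**6. Cost of also requiring both group intervals inside ±0.075.** With no true effect in either group and equal weights, the pooled 90% interval lies inside with probability .95. Each group's half-width is 1.645 × 0.0294 = 0.0484, so its estimate must lie within ±0.0266 (probability .63). Both together: .63² = .40. With 95% intervals the fall is from .90 to .44² = about .20.

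**The case against.** Five points can be made for the plan.

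- **A reader might infer that the plan has chosen a pooled final analysis.** It has not: pooling appears only in the sample size simulation, and no reflex model is given. What stands is that the only basis described is pooled.
- **A reader might take the .56 as the plan's own error rate.** The plan states no equivalence test, interval rule or level. It speaks of power to detect, and its central hypothesis is that hormones do alter motor control. The figure illustrates one way a null could be read, and it falls to .10 if nOC women carry most of the weight. That same weighting makes the OC-nOC difference harder to estimate, so it does not help the missing contrast.
- **A reader might take different associations in the two groups as established.** The hopping result in Section 2.a makes them plausible for reflexes, no more.
- **The intended contrast may not be an interaction.** The assays listed in Section 4.d are estradiol, progesterone and testosterone, so a correlation in OC women need not measure the effect of exogenous hormones. The contrast could be reflex level or variability. This stands, and the remedy must leave room for it.
- **The analysis may be described elsewhere.** Some pages and figures are not public, and the form in Section 2 allows reference to a full protocol or grant application. Absence can be judged only on the text available.

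**Conclusion.** The concern holds in limited form. The documents make the OC-versus-nOC contrast part of Aims 1 and 2 but give it no analysis and no power, and the .95 belongs only to the pooled average. For a difference of 0.075, power would be .44 at best among the weightings examined (.50 if one-sided) and as low as .19. A pooled null could miss an association confined to nOC women: pooled power would run from .44 to .90, depending on how the estimator weights the groups. These figures rest on taking .95 as correct, alpha 0.05, and zero association in OC women.

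It does not follow that pooling is wrong, or that a pooled rule-out is invalid for the average over both groups. The mismatch between daily reflexes in the simulation and every-other-day testing in Procedures Involved ("all female subjects, both OCs and nOCs, will undergo every other day testing as described in Aims 1 and 2") is a separate issue and adds no weight here. The point should be fixed; confidence is medium because part of the source is not available.

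**What to change.** Keep the pooled estimate, and make these changes:

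1. Name the within-person model for the reflex outcomes in Aims 1 and 2, include a hormone-by-contraceptive-group interaction, and report the OC and nOC associations separately with confidence intervals. If the intended contrast is reflex level or variability, say so and specify that instead.
2. State that the .95 applies only to the pooled average. Give nOC-only and interaction precision from the same simulation, with alpha and sidedness stated.
3. Limit any rule-out from the pooled result to the average over both groups. Word conclusions about nOC women from their own interval, without making the group-specific intervals a veto on the pooled conclusion; step 6 of the working shows how much that veto would cost.

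The cost is naming a model, one added term and two further outputs from the simulation, with no change to enrolment or visits. The downside is candour about precision: stated power at 0.075 will be below .95 for nOC women alone and for the interaction. A rule-out specific to nOC women will often not be reached with 30 women: at equal weights and no true effect, the probability is .63 with a 90% interval or .44 with a 95% interval.
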